Another factor that complicates prevalence estimates of aTB is that various screening and diagnostic algorithms are currently in use. Most prevalence surveys use either the presence of symptoms or lung field abnormality on chest x-ray to trigger collection of sputum, which is then subjected to NAAT. Because of its cost and requirement for laboratory infrastructure, sputum MGIT is rarely performed at scale, but when it is, it identifies additional cases of bacteriologically-confirmed TB¹⁴.

The efficiency of chest x-ray surveys to detect asymptomatic TB has been greatly enhanced by the development of portable hardware for the capture of high-quality digital chest x-ray images and the development of computer-assisted diagnostic algorithms that can identify lung field abnormalities suggestive of TB with comparable accuracy to human radiologists^{15, 16}. Despite their efficiency, surveys in which sputum collection is triggered by chest x-ray, fail to detect the subpopulation of people with asymptomatic TB who have normal chest x-rays (recently shown by Mendelsohn et al. to comprise up to 43% of asymptomatic bacteriologically-confirmed TB among household contacts of a symptomatic index case)¹⁷. Chest x-ray screening surveys also identify people with chest x-rays suggestive of TB whose screening sputum tests are negative. This group presents a diagnostic and management challenge to health systems because the chest x-ray abnormalities of people in this group may be attributable to early progressive TB, inactive previously treated TB, non-TB infectious or non-infectious aetiologies. The stochasticity of sputum sampling and the limited sensitivity of sputum Xpert and MGIT for paucibacillary TB, means that collection of additional sputum samples for microbiologic evaluation would confirm TB-C in a proportion of these individuals. This knowledge and information about the proportion of the remaining TB-U group that progressed to bacteriologically-confirmed TB in the year after screening is important unknown information to guide future screening efforts. Addressing key knowledge gaps about the comparative performance of existing diagnostic tests to identify aTB and the characteristics and outcomes of sub-groups identified by different combinations of these tests can be addressed through a large-scale screening study that collects sputum for Xpert and MGIT and dCXR on all participants.

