		
3. Participants selected as healthy controls
 
Inclusion criteria
 
 1. Adolescent/adult participant in TB screening 2. Screening W4SS negative 3. Screening sputum Xpert negative; AND Mtb MGIT negative* 4. Selected as a healthy control in the Cross-sectional study of Mtb infection in households (see above) 
ALL 3 groups above
 
Exclusion criteria
 
 1. Unable or unwilling to consent 
* MGIT results returning after enrolment may result in study group re-categorisation

Cohort study (sub-study 2)	Adolescents and adults (≥ 15 years) who participated in TB screening.	
Participants who meet the study case definition for bacteriologically-unconfirmed TB (TB-U)
 
Inclusion criteria:
 
 1. Adolescent/adult participant in TB screening 2. All three sputa Xpert are negative/ ‘trace’ AND all three sputum are Mtb MGIT negative 3. Screening dCXR/CAD interpretation is “suggestive of TB” 4. Clinical assessment at phenotyping visit does not suggest a non-TB aetiology for dCXR/CAD findings and is consistent with TB-U 5. Participant did not commence TB treatment after phenotyping visit 
Exclusion criteria
 
 1. Unable or unwilling to consent to longitudinal follow-up

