Case-control phenotyping study (sub-study 1) AND Cohort study (sub-study 2)	
Visit 1.1 Facility based clinical assessment (weeks 1-8)
 
 • Individual consent/ assent • Referral to research clinic for phenotyping 
 ◦ Blinded structured questionnaire, include symptoms, quality of life, health outcomes ◦ Physical examination ◦ Collection of 2 sputum samples (Xpert, MGIT culture)* ◦ Collection of samples for novel diagnostic tests 
 ▪ Tongue swabs ▪ Facemask ▪ Exhaled breath condensate ▪ Venous blood – HIV; VL; HbA1C; FBC/smear; Mtb cell free DNA; Mtb-specific T cell activation, biobanking specimens ◦ Physician review of participant's TB screening results • Clinical referral for TB and non-TB care • Telephonic review of linkage to care and well-being • Electronic / physical record review to confirm TB treatment initiation and completion
TB-U Cohort study (sub-study 2)	
Visit 1.2, to 1.5: Longitudinal follow-up (Months 3, 6, 9 & 12)
 
 • Clinical assessment including symptoms, quality of life, health outcomes • Physical examination • Sputum samples x 2 (Xpert, MGIT culture) • Venous blood – Mtb cell free DNA; Mtb-specific T cell activation, biobanking specimens • Digital chest x-ray • Facemask and Exhaled Breath Condensate, in a subset of participants • Physician review • Clinical referral for TB or non-TB care

Tongue swabs will only be collected if approved by WHO and/or national authorities (South Africa or Indonesia) and in participants unable or refuse to produce sputum

* If eligibility is based on a positive tongue swab collected due to unsuccessful sputum collection at visit 1.0, three sputum samples will be collected at visit 1.1

[figure not shown]
\$ HIV testing in children will only be performed in South Africa

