Eligible participants for this TB-U cohort study will be evaluated in the research clinic every three months (month 3,6,9 &12) for one year (**Visits 1.2-1.5**) to monitor progression.

At each follow-up visit, participants will undergo a structured clinical assessment, including an interim health history, review of recent antibiotic or TB treatment use, detailed symptom screening, evaluation of quality of life, functional status, and health-seeking behaviour.

A comprehensive physical examination will be performed, including assessment of vital signs, height, weight, lymphadenopathy, and breath sounds.

Sputum specimens will be collected for TB phenotyping, consisting of two samples, either an early-morning and spot specimen or two spot specimens, as per site procedures. Venous blood will be drawn for phenotyping assays, including Mtb-specific T cell activation, Mtb cell-free DNA, and samples for biobanking. A dCXR/CAD will be performed at each visit. Facemask and Exhaled breath condensate will be collected from a subset of participants

A study physician will regularly review each participant's clinical, radiological, and microbiological results, including sputum findings, to assess disease progression or resolution. If a positive sputum result is identified at any time, the participant will be promptly contacted and referred for TB evaluation and treatment initiation in line with national guidelines. Referrals will be made for non-TB care as required. Ongoing contact will be maintained with all participants referred for TB treatment to encourage initiation of TB treatment and to continue to assess participant well-being until linkage to care and commencement of TB treatment is documented (verification by chart review or electronic record linkage). Individuals who commence TB treatment during follow-up will be considered to have reached the progression endpoint and will not continue with further TB-U cohort study visits.

Visit 1.5 will serve as the End-of-Study visit for participants in Sub-study 2. At this visit, clinically relevant results will be returned, participants will be counselled to seek clinical care if any symptoms or physical conditions worsen, and they will be thanked for their participation

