We will use survival analysis methods to estimate the time to progression. The primary progression endpoint will be defined as a positive sputum test. An alternative progression endpoint will include worsening of symptoms or clinical status, radiological progression and/or starting TB treatment. Person-time will be calculated from date of entry to the TB-U cohort until the earliest of date of the progression endpoint, the last visit seen, or death. Participants who have not met the progression endpoint by the end of follow-up will be censored administratively at the date of the 12-month visit. Since we expect <15% to progress (based on published data), we will use restricted mean survival time (RMST) to estimate the average survival over follow-up. We will use linear regression to compare log-transformed plasma biomarkers between progressors and non-progressors, assuming a normal distribution, or Wilcoxon rank sum tests if data are non-normally distributed. Biomarkers that are measured as binary variables will be compared between groups using Chi-squared tests. Factors associated with time to progression will be explored using Cox regression.

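### TB-U cohort: one positive follow-up sputum counts as progression from entry onward, so some TB missed by the three entry sputa will be counted as progression, in an unknown amount

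*Protocol*

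**What the plan says.** Section 5.2 defines the outcome of sub-study 2: "The primary progression endpoint will be defined as a positive sputum test". Person-time starts at entry to the TB-U cohort. An alternative endpoint brings in worsening symptoms or clinical status, radiological progression and starting TB treatment.

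Table 2 (section 3.4) gives the sampling: "Visit 1.2, to 1.5: Longitudinal follow-up (Months 3, 6, 9 & 12"), with "Sputum samples x 2 (Xpert, MGIT culture") at each visit. Section 3.5 agrees: "Sputum specimens will be collected for TB phenotyping, consisting of two samples".

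Entry to the cohort (Table 1, section 3.3) requires: "All three sputa Xpert are negative/ ‘trace’ AND all three sputum are Mtb MGIT negative". A footnote to the Case Definitions accepts one contaminated culture if the other two are negative and all three Xpert results are negative.

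The Background says sputum sampling is stochastic and that Xpert and MGIT have limited sensitivity for paucibacillary TB. Hence "collection of additional sputum samples for microbiologic evaluation would confirm TB-C in a proportion of these individuals". The individuals meant are "people with chest x-rays suggestive of TB whose screening sputum tests are negative". As a separate unknown it names "the proportion of the remaining TB-U group that progressed to bacteriologically-confirmed TB in the year after screening". The Stage Gate text in section 5.1 keeps the same two quantities apart.

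**The concern.** A positive sputum at month 3 or later can mean two things. The disease may have advanced since entry, or it may have been present and stable at entry and been found only because more samples were taken. The protocol recognises this distinction for the step from screening to Visit 1.1. It does not carry it into follow-up, where eight further sputa are collected and the first positive is the event. No second positive, change from baseline or separate handling of early positives is asked for. The alternative endpoint, on its natural reading, adds further kinds of event and does not narrow the primary one.

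Two results are at stake. The one-year progression risk in untreated TB-U would be somewhat too high. More importantly, section 5.2 compares plasma biomarkers between progressors and non-progressors. If some progressors had TB at entry that three sputa missed, a marker that separates the groups may be diagnosing prevalent disease and not predicting progression. Secondary objectives 3 and 4 (longitudinal outcomes; correlates of progression and resolution) need the prognostic answer.

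**Working it through.** **1. Follow-up sputa.** 4 visits × 2 = 8 per person (Table 2).

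**2. The protocol's own figures.** Section 5.1 assumes an annualized rate of 10% (6.2 to 13.3%) in 500 people per site. 500 × 0.062 = 31.0 and 500 × 0.133 = 66.5, which reproduces 31-66. The biomarker power (50 progressors, 100 non-progressors, 0.50 SD; two-sided 5% assumed, as no alpha is stated) is Φ(0.5/√(1/50 + 1/100) − 1.96) = Φ(2.887 − 1.960) = 0.82, in line with the stated 80% or more.

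**3. Disease left after entry.** Two inputs are not in the protocol and are assumed: π, the share of candidates with stable baseline TB before any sputum, and s, the chance that one sputum detects it. Sputa are taken as independent.

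- Residual share after three negative sputa: r = π(1−s)³ / [1 − π + π(1−s)³]
- Late detections in follow-up: 500 × r × [1 − (1−s)⁸]
- Of these, found at month 3: 500 × r × [1 − (1−s)²]

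Example, π = 0.10 and s = 0.2: r = 0.0512/0.9512 = 0.054; 1 − 0.8⁸ = 0.832; 500 × 0.0538 × 0.832 = 22.4.

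With π = 10%:

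| s | r after three sputa | Late detections per 500 | At month 3 (share) | Late detections if entry used one sputum |
|---|---|---|---|---|
| 0.2 | 5.4% | 22.4 | 9.7 (43%) | 34.0 |
| 0.3 | 3.7% | 17.3 | 9.4 (54%) | 34.0 |
| 0.5 | 1.4% | 6.8 | 5.1 (75%) | 26.2 |
| 0.7 | 0.3% | 1.5 | 1.4 (91%) | 16.1 |

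The last column replaces (1−s)³ by (1−s) and shows what the three-sputum rule achieves. At s = 0.5 it cuts the count from 26 to 7. At s = 0.2 it cuts it only from 34 to 22.

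**4. Wider range.** Over π = 5 to 30% and s = 0.1 to 0.7, the count with the three-sputum rule runs from under 1 to about 75 per 500.

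**5. Against the expected events.** 22 late detections equal about a third of 66 (22/66 = 33%) and about seven-tenths of 31 (22/31 = 71%). The 1.5 at s = 0.7 equals 2 to 5%. The protocol does not say whether the published rate behind 31-66 already contains late detections, so these are comparisons of scale and not shares of a known total.

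**6. Cost of setting month 3 aside.** If true events fell evenly over the year, a quarter would be at month 3: 31-66 becomes 31 × 0.75 = 23 to 66 × 0.75 = 50. With 50 × 0.75 ≈ 38 progressors against 100, power for 0.50 SD is Φ(0.5/√(1/38 + 1/100) − 1.96) = Φ(0.664) = 0.75.

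**The case against.** The strongest reply is the entry rule. A reader might infer from the Background sentence that the whole yield of repeat sampling is booked as progression. The protocol does not support that. The sentence concerns people with a negative screening sputum, before the two Visit 1.1 sputa; those sputa are the protocol's answer, and only people who pass all three enter the cohort. Only a residue is at issue, and at s of 0.5 or more it is small. This part stands.

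A reader might also infer that the primary endpoint is wrong and should be replaced. That too goes further than the text allows. The Protocol Summary asks for time to microbiological progression, section 5.1 counts progressors to microbiologically confirmed TB, and the case definition of confirmed TB accepts one positive sputum of three. One positive is therefore the protocol's own step from unconfirmed to confirmed. It shows current disease, though not that the disease is new or worse since entry.

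The remaining objections stand in part.

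- A sensitivity analysis may be left to a SAP that is not shown, and its absence alone is no error. The endpoint and the start of person-time are fixed in section 5.2, however, and that section already names an alternative progression endpoint and plans misclassification analyses for the core study.
- Splitting off month 3 discriminates poorly at low detection. At s = 0.1, 33% of late detections fall there (0.19/0.570), against 25% for evenly spread true events. It works better at s of 0.3 or more.
- Corroboration by X-ray or symptoms would miss asymptomatic bacteriological progression. The Background itself cites up to 43% normal X-rays in asymptomatic confirmed TB among household contacts.

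The entry filter is also not airtight. Trace results are allowed and one contaminated culture can be accepted.

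**Conclusion.** The concern holds in a limited form. Section 5.2 counts any single positive among up to eight sputa as progression, and nothing in the protocol separates late detection of baseline disease from progression during follow-up, although the Background and the Stage Gate treat them as different quantities. The three-sputum rule removes much of the problem but not all of it when detection per sputum is low.

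The size is unknown. At an assumed 10% baseline disease it is about 22 per 500 at s = 0.2 and 1.5 at s = 0.7. These counts rest on assumed π and s, independent sputa, and baseline disease that neither advances nor clears within the year. They peak near s of 0.1 to 0.2, so variation in detection between people could move them either way. The Stage Gate estimate of the yield of the two additional sputa would help narrow the range. There is no contradiction or arithmetic error here. The main exposure is the interpretation of the biomarker comparison.

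**What to change.** Keep any positive sputum as the primary microbiological endpoint. In section 5.2, add:

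1. A pre-specified sensitivity endpoint: a positive sputum plus at least one corroborating finding from data already collected, namely a second positive sputum or test, dCXR/CAD worse than the screening film, or new symptoms. Because people who start treatment leave the cohort visits (section 3.5), a second positive will mostly have to come from the same visit, and the definition should allow for this.
2. Month-3 positives reported separately from those at months 6-12.
3. The biomarker comparison repeated on the stricter endpoint, and again without month-3 events.

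This needs no new visit or sample. The cost is fewer events: power for 0.50 SD falls from 82% to about 75% if a quarter of 50 progressors is set aside. Some true asymptomatic progression would also be excluded from the stricter endpoint. Both are reasons to run these analyses beside the primary one and not in its place.

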3.8 STUDY OUTCOMES/ ANALYSES

The study is designed to assess both the transmission of Mtb within households and the diagnostic performance of current and novel tools for detecting asymptomatic TB. The outcomes are grouped into primary and additional outcomes categories as outlined below.

CORE STUDY

Primary endpoint: Cumulative prevalence of child household contact IGRA positivity or confirmed TB (TB-C) at 10 weeks after diagnosis of the index case.

Additional outcomes/ analyses:

- (1) Proportion of children that convert from negative IGRA status at baseline to a positive IGRA status at 10-week visit.
- (2) Proportion of children with a positive plasma cell free Mtb DNA assay and positive Mtb-specific T cell activation assay, stratified by household group.
- (3) Whole genome sequencing of Mtb isolates from people with TB-C and household contacts.

CASE-CONTROL PHENOTYPING STUDY (SUB-STUDY 1)

- (4) Sensitivity, specificity, positive predictive value, negative predictive value, yield, feasibility, acceptability of digital chest x-ray with computer aided diagnosis (dCXR/CAD), sputum Nucleic Acid Amplification Test (NAAT), Mycobacteria Growth Indicator Tube (MGIT), tongue swab NAAT, and bioaerosol collection facemask mask NAAT to detect aTB-C.
- (5) Symptoms, health outcomes quality of life, comorbidities, nutritional status, and TB history, relative to group and W4SS status at screening.

(6) Proportion and characteristics of participants with detectable exhaled breath condensate lipoarabinomannan (LAM), positive plasma cell free Mtb DNA assay, positive Mtb-specific T cell activation assay and additional blood-based TB biomarkers, stratified by group.

TB UNCONFIRMED (TB-U) COHORT (SUB-STUDY 2)

(7) Time to event and factors associated with microbiological or clinical progression in participants with initially untreated aTB-U.

(8) Plasma biomarkers (including cell free Mtb DNA, Mtb-specific T cells, transcriptional signatures) that correlate with progression from aTB-U in the 12 months after TB screening

(9) Proportion and characteristics of participants with TB screening results suggestive of (TB-U) who have a subsequent positive sputum GeneXpert Ultra, sputum MGIT, tongue swab NAAT or Bioaerosol collection facemask mask NAAT.

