APPENDIX B: TB NOTIFICATIONS AND BURDEN IN INDONESIA AND SOUTH AFRICA

Table 6: TB notifications and estimated TB Burden in Indonesia and South Africa in 2023¹

	Indonesia	South Africa
Total TB incidence (n)	1.1M (995K-1.2M) *	270K (168K-395K) *
Total TB incidence rate per 100 000	387 (354-432)	427 (265-626)
HIV negative TB mortality	125K (108K-143K) *	25K (23K-26K) *
HIV positive TB mortality	6.2K (5.3K – 7.1K) *	31K (9K-66K) *
TB Notifications		
New and Relapse Cases (n)	804.8K *	211.8K*
New and Relapse Cases rate per 100 000	286/ 100 000	335/100 000
Percentage of new and relapse tested with rapid diagnostics at diagnosis	57%	83%
Total cases notified (n)	821.2K*	222K*
Percentage new and relapse with known HIV status	61%	84%
People with TB with known HIV-positive status	3.5% (16.2K*)	54% (95.8K*)
Estimated percentage of new TB cases with MDR/RR-TB	2.1% (2-2.1)	3.1% (3.1-3.2)

Note: *Number: K= 000 or M= 000 000; ^Rate: (no. per 100 000 population per year

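### TB-U cohort: death ends person-time but is in neither progression endpoint, so a TB death between visits with no earlier recorded event is censored in the clinical progression analysis

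*Protocol*

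**What the plan says.** Protocol section 5.2 (TB-U cohort, sub-study 2) sets two endpoints. On the primary: "The primary progression endpoint will be defined as a positive sputum test". On the other: "An alternative progression endpoint will include worsening of symptoms or clinical status, radiological progression and/or starting TB treatment". Neither names death.

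The same paragraph sets the follow-up rule: "Person-time will be calculated from date of entry to the TB-U cohort until the earliest of date of the progression endpoint, the last visit seen," with death as the third alternative. Death is thus listed apart from the progression endpoint and beside the last visit seen. The administrative rule is: "Participants who have not met the progression endpoint by the end of follow-up will be censored administratively at the date of the 12-month visit". On the summary measure: "we will use restricted mean survival time (RMST) to estimate the average survival over follow-up". Cox regression is planned for factors associated with progression, and plasma biomarkers are compared between progressors and non-progressors.

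Elsewhere in the Protocol:
- Section 3.8, outcome 7, gives the aim as "Time to event and factors associated with microbiological or clinical progression in participants with initially untreated aTB-U".
- Table 1 (section 3.3) requires that participants did not start TB treatment after the phenotyping visit.
- Section 3.5 schedules visits at months 3, 6, 9 and 12 and treats starting TB treatment during follow-up as reaching the progression endpoint. It does not mention death there.

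**The concern.** The cohort is untreated at entry and seen every three months, so a participant can deteriorate and die between visits. Under section 5.2 that death is a non-event exit, handled like a last visit. For an endpoint meant to capture clinical progression, this ranks outcomes unevenly: starting treatment counts as progression, while dying of TB before anything else is recorded does not.

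Censoring such a death lets the participants still at risk stand in for the person who died. That is unreasonable when the death is itself the extreme form of the outcome. At stake are the clinical-progression estimates and the make-up of the non-progressor group in the biomarker comparison, which could contain some fatal progressors. The co-primary objectives are not touched.

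**Working it through.** **1. The plan's own figure.** Section 5.1 expects 31–66 progressors to microbiologically confirmed TB per site, from 500 participants and an annualised rate of 10% (95% CI 6.2–13.3). 500 × 0.062 = 31.0 and 500 × 0.133 = 66.5, so the figure reproduces as a simple product, with no allowance for death or loss.

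**2. How death is handled.** Person-time has three ends: progression endpoint, last visit seen, death. Since death is separate from the endpoint and in neither definition, it ends follow-up without an event. The protocol uses the word censored only for the 12-month cut; for death it is an inference, but no other reading fits the list.

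**3. Model.** Constant hazards over one year: progression to positive sputum λ = 0.10 (section 5.1); TB death without prior positive sputum d = 0.005, 0.01 or 0.02. The values of d are assumptions, because the protocol gives no mortality rate for this cohort.

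- Expected deaths per 500 = 500 × d/(λ+d) × (1 − exp(−(λ+d)))
- Cumulative incidence of positive sputum with death competing = λ/(λ+d) × (1 − exp(−(λ+d)))
- Same quantity with deaths censored = 1 − exp(−λ) = 1 − exp(−0.10) = 9.52%

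| d per year | Deaths per 500 | Sputum progressors per 500 | Incidence, death competing | Incidence, death censored |
|---|---|---|---|---|
| 0.005 | 2.4 | 47.5 | 9.49% | 9.52% |
| 0.01 | 4.7 | 47.3 | 9.47% | 9.52% |
| 0.02 | 9.4 | 47.1 | 9.42% | 9.52% |

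At d = 0.02: 0.10/0.12 × (1 − exp(−0.12)) = 9.42%. For the primary endpoint, censoring deaths therefore overstates cumulative incidence by 9.52 − 9.42 = 0.10 percentage point at most in this range.

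**4. The alternative endpoint.** The 2.4–9.4 deaths are an upper bound on missed events. Any of these participants with recorded worsening, radiological progression or treatment start before death already counts. If half did, 1.2–4.7 deaths per 500 would be missed. The documents give no figure for this fraction.

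**5. Biomarker comparison.** Section 5.1 assumes 50 progressors, 100 non-progressors and a difference of 0.50 SD. Two-sample t power is 81.8%. If 1% or 3% of the non-progressor group are really fatal progressors, the mean difference shrinks to 0.50 × 0.99 = 0.495 SD or 0.50 × 0.97 = 0.485 SD, and power to 81.0% or 79.4%. For scale, 9.4 deaths among 500 − 47.1 = 452.9 sputum-negative participants is 2.1%.

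**The case against.** The strongest case against is that the primary endpoint is a positive sputum test, and someone who dies without one has not had that event. Ending person-time at death gives a valid cause-specific hazard, so the planned Cox model for that endpoint needs no change. This stands.

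Two stronger readings are tempting, and the documents support neither.
- A reader might infer that 12-month progression is understated, as 9.5% instead of up to 1 − exp(−0.12) = 11.3% at the 2% rate. That sets positive sputum against positive sputum or TB death. These are different endpoints, and the gap is not bias in the first.
- A reader might take the mortality rows of Appendix B, Table 6 (such as "HIV positive TB mortality"), form deaths-to-incidence ratios and apply them to the 31–66 progressors. Those progressors have positive sputum and are already events. The table is national and says nothing about sputum-negative people found by X-ray.

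The alternative endpoint is also partly protected. Each visit includes symptoms, examination, two sputa, X-ray and physician review, and worsening of clinical status could be stretched to cover death. The first narrows the gap to deaths with no earlier recorded event. The second sits badly with death being listed separately.

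Finally, competing-risk reporting and the classing of early exits in the biomarker groups may be in an analysis plan that is not shown. That is fair for those details. It does not cover the person-time rule and the endpoint definitions, which the protocol itself fixes.

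**Conclusion.** The point holds for the alternative clinical endpoint and, as a possibility, for the biomarker grouping, where section 5.2 does not say how early deaths are classed. The primary positive-sputum endpoint is not materially biased.

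The size is modest and rests on assumption: at most about 2–9 missed events per 500 if TB deaths without prior positive sputum run at 0.5–2% per year with constant hazards, and fewer to the extent that worsening was recorded first. The effect on biomarker power is small. A reader might also infer that deaths will go unreported. The protocol does not say so, and its person-time rule already requires dates of death. This is a cheap improvement to an analysis definition in a sub-study.

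**What to change.** In section 5.2, TB-U cohort:

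(a) Count death that is attributed to TB, or where TB is not excluded, as an event on its date in the alternative clinical progression endpoint. Add an all-cause version as a sensitivity analysis, and use all-cause death where cause is not available.

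(b) For the positive-sputum endpoint, report cumulative incidence with death as a competing event and state the number of deaths. Leave the Cox model as it is, described as cause-specific.

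(c) Do not class participants who died before the 12-month visit without a positive sputum as non-progressors in the biomarker comparison.

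The cost is a few sentences and a little more analysis. Dates of death are already needed. Cause of death is the weak spot: the visit schedule does not collect it, access to health-service records is described only for South Africa (section 7.3), and reviewing deaths is not among the Clinical Safety Committee's listed duties (section 8.3). Cause will be uncertain for a few participants, which the all-cause version covers. These changes concern analysis only; no clinical rule is proposed.
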